8.1 Sample Size

The sample size was determined from expected changes in the primary endpoint: the change from baseline in cartilage thickness in the total femorotibial joint as evaluated by MRI at 2 years.

[figure not shown]
This trial is set up to detect a potential dose relationship, based on the total dose of sprifermin received over the 2 years, in limiting the reduction of or increasing the cartilage thickness in the total femorotibial joint, assuming:

- A mean change from baseline at 2 years of
 - -0.03 mm in the placebo group (i.e., 0 mcg over 2 years)
 - -0.01 mm in the sprifermin 30 mcg once a year group (i.e., 180 mcg over 2 years)
 - +0.01 mm in the sprifermin 30 mcg twice a year group (i.e., 360 mcg over 2 years)
 - +0.01 mm in the sprifermin 100 mcg once a year group (i.e., 600 mcg over 2 years)
 - +0.03 mm in the sprifermin 100 mcg twice a year group (i.e., 1200 mcg over 2 years)
- A common SD (standard deviation) of 0.10 mm
- A type-one error, α , of the primary efficacy analysis set at 5% two-sided
- Normal distribution.

The above assumptions were based on available MRI data from the OAI (<http://oai.epi-ucsf.org/datarelease/>) and from the POC trial (28980; see [Figure 3](#)).

A minor deviation from linearity has been introduced in these hypotheses based on the expectation of similar changes for the sprifermin 30 mcg twice a year and sprifermin 100 mcg once a year groups. Indeed, according to the current knowledge of the biological mechanism of action of sprifermin, the treatment effect of the highest dose (100 mcg) given once a year could be similar to that of a lower dose (30 mcg) given twice a year. Moreover, the variability of the measure is large, and therefore a deviation from perfect linearity may be expected.

Figure 3 **Expected Mean Changes in Cartilage Thickness (mm) in Total Knee at 2 Years (SD = 0.10)**

OA: osteoarthritis; POC: proof of concept; SD: standard deviation

Calculations showed that:

- 55 evaluable subjects in each group (total 275 subjects) will ensure a power of 90% for detecting a linear dose relationship using a linear trend test,
- 76 evaluable subjects in each group (total 380 subjects) will ensure a power of 90% for detecting an overall treatment effect (meaning that at least one group differs from the other groups) as well.

Based on recent literature and other trial experience (45, 46), the subject discontinuation rate is estimated to be close to 30% at two years. Assuming a 30% drop-out rate, a total of 545 subjects should be randomized (109 subjects per group) in order to detect an overall treatment effect.

In order to be able to demonstrate that structure improvement translates into symptomatic benefit, it is important that the study be adequately powered to detect significant differences in normalized WOMAC scores. With 76 evaluable subjects per treatment group, the power to show a statistically significant difference between at least one active treatment group and the placebo group for the secondary WOMAC endpoints ranges from 69% to 87% for the total score, from 80% to 99% for the pain score and from 53% to 83% for the function score, depending on the expected mean difference from placebo (see Table 3).

Table 3 Power Calculations for Pairwise Differences (Sprifermin versus Placebo) on Normalized WOMAC Scores with 76 Evaluable Subjects per Treatment Group

	Expected mean difference from Placebo	Common SD	Power
Total Score - Normalized (range 0-100 points)	8 points	20	69%
	9 points		79%
	10 points		87%
Pain Score - Normalized (range 0-100 points)	10 points	22	80%
	15 points		99%
Function Score - Normalized (range 0-100 points)	7 points	21	53%
	9 points		75%
	10 points		83%

SD: standard deviation; WOMAC: Western Ontario and McMaster Universities Osteoarthritis Index

For reference, a difference of 10 points from placebo in the normalized WOMAC scores is considered as clinically meaningful (highlighted in bold type in the table).

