Statistical methods (includes sample size calculation)	
Sample Size Calculation
 
The number of 545 randomized subjects has been calculated to provide 90% power to detect a dose relationship as well as an overall treatment effect in the change from baseline in cartilage thickness in the total femorotibial joint at 2 years, assuming a discontinuation rate of 30% at that time. The study is also adequately powered to detect significant difference in at least one active treatment group and the placebo group for a secondary WOMAC endpoint such as the pain, function or total WOMAC score.
 
Statistical Methodology
 
The treatment effect on the primary endpoint will be assessed through dose-ranging using a repeated measurement analysis of variance (ANOVA, using PROC MIXED in SAS) on absolute change from baseline, including the baseline value, the treatment group, the time, and the country as factors and treatment by time as interaction.
 
The primary efficacy analysis will consist of testing the linear dose relationship and the overall treatment effect at 2 years. The significance level will be set at 5% two-sided for both tests.
 
Pairwise comparisons (sprifermin versus placebo, and between sprifermin dose and regimen groups) will be performed within the context of this modeling framework. For each pairwise comparison, the difference between treatments and the corresponding 95% confidence interval (CI) and p-value will be presented.

	
The same ANOVA model used for the primary endpoint will be used to assess the treatment effect on continuous secondary endpoints such as MRI endpoints, WOMAC endpoints (total, pain, function, and stiffness scores), and X-ray endpoints at each time point and over time.
 
Logistic regression will be used to assess the treatment effect on the binary efficacy endpoints such as the OMERACT-OARSI responder rate. Point estimates for each pairwise comparison and corresponding 95% CIs and p-values will be provided.

--	---

2 Sponsor, Investigators and Trial Administrative Structure

Sponsor

For countries other than the United States of America, the Sponsor of this trial is Merck KGaA, [name].

For the United States of America, the Sponsor of this trial is EMD Serono Inc. ([name]).

Sponsor Responsibilities

The sponsor will be responsible for overseeing all aspects of the study.

External Service Providers

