significant difference between at least one active treatment group and the placebo group for the secondary WOMAC endpoints ranges from 69% to 87% for the total score, from 80% to 99% for the pain score and from 53% to 83% for the function score, depending on the expected mean difference from placebo (see Table 1).

Table 1 Power Calculations for Pairwise Differences (Sprifermin versus Placebo) on Normalized WOMAC Scores with 76 Evaluable Subjects per Treatment Group

	Expected mean difference from Placebo	Common SD	Power
Total Coons Name discal	8 points	20	69%
Total Score - Normalized (range 0-100 points)	9 points		79%
(range o- roo points)	10 points		87%
Pain Score - Normalized	10 points	22	80%
(range 0-100 points)	15 points		99%
Function Score -	7 points	21	53%
Normalized	9 points		75%
(range 0-100 points)	10 points		83%

SD: standard deviation; WOMAC: Western Ontario and McMaster Universities Osteoarthritis Index

For reference, the minimally clinically important difference (MCID) in WOMAC scores is considered to be about 10% of the maximum score, which correspond to approximately 10 points for the total WOMAC score, 7 points for the WOMAC function index (activities of daily living) score, 2 points for WOMAC pain index score, and 1 point for the WOMAC stiffness index score) [1]. WOMAC scores that are considered MCID are highlighted in bold type in the table above.

Please note that the power calculations did not include adjustment for multiplicity. Randomization is described in Section 6 of the protocol.

8 Overview of Planned Analyses

[figure not shown]
The protocol specifies a two-year treatment phase (Baseline to Year 2) followed by a three-year extension phase (Years 2 to 5). Subjects and sites will remain blind to treatment throughout the entire protocol (Baseline to Year 5). The statistical analysis will be performed in three steps (see "Study Design" figure below):

Reporting of the DBPC treatment phase: After the last subject's last visit of the DBPC treatment
phase, the data collected until the end of the DBPC treatment phase will be cleaned and released,
a Blind Data Review Meeting will be held to clarify potential remaining issues before the
database can be partially locked (this terminology is used here to differentiate data coming from
the DBPC treatment phase vs. extended follow-up phase, but all processes for formal database
lock will be followed); if all participants of the Blind Data Review Meeting are in agreement

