LOCF2 (Up to Month 60)	Last post-baseline measurement in Follow-up period (2, 1849)	50

Adjustment for Multiplicity

The main objective of this Phase II trial is to select a dose regimen for further development in Phase III; therefore, no adjustment for multiplicity (except for dunnett adjustment for multiple comparisons used in the ANOVA models) resulting from multiple endpoints will be made. Caution should be used in interpreting significant p-values (p < 0.05). Interpretation of the results will involve global consideration of all efficacy results obtained in combination with an appropriate judgment of clinical relevance and consistency across endpoints.

Missing Data

As a general rule, all data collected and available will be used in the analysis. In general no imputation of missing data will be applied independently of the statistical method used to analyze the data, see however below remarks for LOCF in summaries over time.

The number of subjects contributing data will decrease over time. In summary assessments by time-point within DBPC, the LOCF method on post baseline observations will be used as sensitivity evaluation, and will be defined as LOCF1 for the 2-year analysis, and LOCF2 for the

analysis of the extended follow-up. These will only be included in summary tables (not in proc mixed models) and are considered exploratory and will be utilized for phase III statistical consideration. In the remainder of the SAP, if not otherwise stated, LOCF refers to both LOCF1 and LOCF2. Details for derivation of LOCF1 and LOCF2 for corresponding endpoints are provided in Table 3, 3a, and 3b.

Exceptions are handling of missing data from questionnaires where the guide for analysis prescribes otherwise, e.g. calculation depending on whether only single items are missing or a complete questionnaire is missing. If only single items are missing, the rules defined by the authors of the questionnaires (if any) will be followed.

The number and percentage of subjects with missing data for the primary and the secondary endpoints medial and lateral cartilage thickness, will be summarized by treatment group and timepoint for the mITT Analysis Set.

Listing of data

In general, all data will be listed by treatment group, subject and time point. Age, sex and race will be displayed in all listings.

ANOVA models

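### The WOMAC power figures are for one unadjusted pairwise comparison, but the text presents them as power for at least one active group, and the SAP did not update them after adding Dunnett

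*Protocol*

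**What the plan says.** Protocol 8.1 gives, for 76 evaluable subjects per group, "the power to show a statistically significant difference between at least one active treatment group and the placebo group" on the WOMAC secondary endpoints, and says that it "ranges from 69% to 87% for the total score, from 80% to 99% for the pain score and from 53% to 83% for" (this last range belongs to function). The table below that sentence is titled "Power Calculations for Pairwise Differences (Sprifermin versus Placebo) on Normalized WOMAC Scores with 76 Evaluable Subjects per Treatment Group". The synopsis states without figures: "The study is also adequately powered to detect significant difference in at least one active treatment group". SAP 7 repeats both sentence and table, and adds: "Please note that the power calculations did not include adjustment for multiplicity".

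On the analysis, protocol 8.5.1 plans no multiplicity adjustment. SAP 11 keeps that position for multiple endpoints, "except for dunnett adjustment for multiple comparisons used in the ANOVA models". Its model code requests Dunnett comparisons with placebo, and SAP 16.2 applies a similar model to the WOMAC total and sub scores. The list of changes from the protocol in SAP 9 does not mention the Dunnett adjustment.

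**The concern.** The sentence and the table attach the same numbers to two different events. The table concerns one active group against placebo. The sentence concerns success in any of four groups, which has a different probability and cannot be computed without saying how many groups are effective. The documents give no such assumption for WOMAC.

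The figures also assume a 5% test of each comparison, whereas the SAP's model code adjusts the comparisons with placebo. Protocol 8.1 calls adequate WOMAC power important for showing that structural improvement translates into symptomatic benefit. A non-significant adjusted comparison could therefore be judged against a power that the comparison does not have.

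**Working it through.** **Inputs.** From protocol 8.1: 76 per group; SD 20 (total), 22 (pain), 21 (function); differences as listed in its Table 3. Five groups with equal allocation (protocol 8.2). No alpha is stated for WOMAC; 5% two-sided is assumed, as for the primary analysis.

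**Formula.** SE = SD × √(2/76). Power = P(|T| > c), where T is noncentral t with noncentrality (difference / SE).

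**Step 1: reproduce the printed figures.** For the total score at 10 points, SE = 20 × √(2/76) = 3.244 and the noncentrality is 10 / 3.244 = 3.082. The normal approximation gives Φ(3.082 − 1.960) = 86.9%; the exact t-test (150 df) gives 86.5%; the table prints 87%. The other seven rows also agree within 1 point (column A). The printed figures are therefore single unadjusted pairwise powers.

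**Step 2: one comparison under Dunnett.** For four comparisons with placebo, equal group sizes and 5 × 76 − 5 = 375 df, the two-sided 5% critical value is 2.452 by simulation. For the total score at 10 points, Φ(3.082 − 2.452) = 74%; noncentral t gives 73.5%. Column B gives all rows.

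**Step 3: at least one significant arm under Dunnett.** This was simulated counting results in the favourable direction, with k arms sharing the stated effect and the rest having none (last three columns).

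| Score, difference | Printed % | A: unadjusted t % | B: Dunnett, one comparison % | Printed − B | k = 1 % | k = 2 % | k = 4 % |
|---|---|---|---|---|---|---|---|
| Total 8 | 69 | 68.8 | 51 | 18 | 51 | 67 | 80 |
| Total 9 | 79 | 78.7 | 63 | 16 | 63 | 78 | 89 |
| Total 10 | 87 | 86.5 | 74 | 13 | 74 | 87 | 94 |
| Pain 10 | 80 | 79.5 | 64 | 16 | 64 | 79 | 89 |
| Pain 15 | 99 | 98.7 | 96 | 3 | 96 | 99 | 99.8 |
| Function 7 | 53 | 53.3 | 35 | 18 | 35 | 50 | 65 |
| Function 9 | 75 | 74.7 | 58 | 17 | 58 | 74 | 86 |
| Function 10 | 83 | 83.1 | 69 | 14 | 69 | 83 | 92 |

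Counting rejections in either direction, the k = 1 figure for the total score at 10 points is 75%. Under a graded pattern (assumed: one quarter, one half, one half and all of the 10 points), at-least-one power under Dunnett is 76% for total, 67% for pain and 71% for function.

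**Step 4: how well 2.452 matches the SAP code.** It is an approximation.

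- The statement with exactly four comparisons averages over visits, so a single-visit SD does not apply. With a constant effect over eight WOMAC visits and within-subject correlation r, the variance is multiplied by (1 + 7r)/8. For r = 0.3 to 0.7 (assumed), 8 points on the total score then has about 93% down to 66% power, against 51% in column B.
- The visit-specific statements use the group-by-visit term and appear to compare every other cell with one placebo cell: 5 × 4 − 1 = 19 comparisons with four visits, or 5 × 8 − 1 = 39 with eight. For 39 comparisons and the same r, the critical value is about 3.0 to 3.1, and 10 points on the total score has about 51% to 54% power, against 74% in column B.

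**The case against.** The strongest reply is that little is hidden and nothing is miscalculated. The table title says pairwise, SAP 7 says the calculations exclude multiplicity adjustment, and the protocol's figures match the protocol's own unadjusted plan. SAP 7 introduces them as the calculation described in protocol 8.1. WOMAC is secondary in a Phase II dose-selection trial, the sample size rests on MRI, and both documents advise caution with p-values. All of this stands. It makes the point one of labelling and of figures not brought up to date.

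A reader might go further and infer that the trial has 3 to 18 points less power than stated to find any effective arm. The documents do not support that. The loss is per comparison and carries over to at-least-one power only if a single arm works. With two arms sharing the effect, the Dunnett figures lie within about 3 points of the printed ones; with four, they exceed the printed figure in every row. A reader might also infer concealment, which the table title and the SAP 7 note rule out.

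The disclosure is nevertheless incomplete. The note does not say that the SAP's own comparisons are adjusted, no adjusted figures are given, the at-least-one wording remains, and the synopsis carries no caveat.

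**Conclusion.** The point holds in this form. The eight WOMAC figures are unadjusted power for one given comparison. They are described as something else in the synopsis, protocol 8.1 and SAP 7, and they do not describe the Dunnett-adjusted comparisons that the SAP specifies. For one comparison at a single time point the shortfall against the printed values is 3 to 18 points. At 10 points, the difference protocol 8.1 calls clinically meaningful, the adjusted figures are 74% (total), 64% (pain) and 69% (function), against 87%, 80% and 83% printed.

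This rests on 5% two-sided alpha, 76 evaluable per arm (approximate, since the repeated-measures model also uses partial data), the planned SDs, and a four-comparison Dunnett adjustment. The LSMEANS statement finally used could move the figures in either direction. Whether at-least-one power falls short depends on the number of effective arms, which the plan does not state for WOMAC.

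**What to change.** - In the synopsis, protocol 8.1 and SAP 7, describe the figures as unadjusted power for a given active group against placebo.
- In SAP 7, add Dunnett-adjusted per-comparison figures, computed for the LSMEANS statement actually used for the Week 104 WOMAC comparison. Confirm how many comparisons that statement covers.
- If an at-least-one figure is kept, state the assumed number of effective arms and their effects.
- Qualify the adequacy claim in the light of the adjusted figures.
- List the Dunnett adjustment in SAP 9 as a change from the protocol.

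The cost is restated text and one recalculated table. Neither the sample size nor the planned analysis changes.

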8.2 Randomization

Randomization will be coordinated centrally, using an IVRS system which will allocate subjects to the treatment groups (see Section 6.3 for further details concerning the technical and logistical aspects of treatment allocation).

Eligible subjects will be randomized to one of the 5 treatment groups with an allocation ratio of 1:1:1:1:1, using a computer-generated randomization list in random permuted blocks.

Randomization will be stratified by country to ensure balance of treatment groups with respect to intrinsic and extrinsic factors that may affect OA outcomes. Moreover, it may not be practical to stratify randomization by site as numbers of subjects in each site are expected to be small.

8.3 Endpoints

8.3.1 Primary Endpoint

The primary endpoint of this trial is the change from baseline in cartilage thickness in the total femorotibial joint as evaluated by MRI at 2 years.

8.3.2 Secondary Endpoints

Secondary efficacy endpoints are:

- Changes from baseline in the WOMAC total score and in the WOMAC pain, function, and stiffness index scores over 2 years
- Change from baseline in the 20-meter walk test over 2 years

- Change from baseline in the PGA over 2 years
- Change from baseline in minimal JSW in the medial and lateral compartments as evaluated by X-ray over 2 years
- Change from baseline in cartilage thickness in the medial and lateral compartments as well as in the total femorotibial joint over 2 years
- Change from baseline in cartilage volume in the medial and lateral compartments as well as in the total femorotibial joint over 2 years
- Synovial fluid levels of sprifermin/FGF-18
- Serum levels of sprifermin/FGF-18

8.3.3 Safety Endpoints

Safety endpoints are:

- Nature, incidence and severity of local and systemic AEs
- Incidence of acute inflammatory reactions (AIRs), defined as increase of pain by 30 mm on a 100 mm VAS associated with a self-reported synovial fluid effusion (i.e., joint swelling) within 3 days following i.a. injection
- Changes in laboratory safety parameters, vital signs, 12-lead ECG parameters, weight, and physical examinations
- Incidence of surgical interventions in the target knee (including any surgical revision, cartilage removal, or any other type of surgical intervention)
- Occurrence of binding and neutralizing antibodies to sprifermin/FGF-18

8.3.4 Exploratory Endpoints

Exploratory endpoints are:

- Outcome Measures in Rheumatology – Osteoarthritis Research Society International (OMERACT-OARSI) responder rate (1) at 2 years
- PGIC over 2 years
- Changes from baseline in the scores of the KOOS QOL and the MOS SF-36 questionnaire over 2 years
- Change from baseline in KOOS Symptom Index over 2 years
- Change from baseline in pain score in the target and contralateral knee over 2 years using an 11-point NRS
- Change from baseline in presence of pain in other joints over 2 years
- Change from baseline in ICOAP scores over 2 years

- Change over time in structural as well as compositional parameters of the knee joint (e.g., synovium, menisci, bone, and other structures) as evaluated by MRI
- Change from baseline in serum, urine, and synovial markers associated with administration of the compound
- Baseline protein markers and/or genetic markers associated with response to treatment or disease progression (response assessed by MRI and/or questionnaire)
- Changes in MRI outcomes, WOMAC scores, 20-meter walk test, PGA, PGIC, JSW, OMERACT-OARSI responder rate, KOOS QOL, KOOS Symptom Index, MOS SF-36, NRS pain score in the target and contralateral knee, presence of pain in other joints, ICOAP, safety laboratory values, and vital signs over the extended follow-up period and nature, incidence and severity of local and systemic AEs during the extended follow-up period (to be summarized descriptively)
- Relationship between dosing (dose and regimen), cartilage structure, and clinical scores as a function of time

The Outcome Measures in Rheumatology – Osteoarthritis Research Society International (OMERACT-OARSI) responder rate (1) will be determined as an exploratory analysis. The OMERACT-OARSI responder criteria involve changes that are deemed to be clinically relevant in three domains: pain, function, and Patient’s Global Assessment. For each of these domains, ranges are defined for absolute and percent changes from baseline that correspond to “high improvement” and “moderate improvement”. OMERACT-OARSI response is defined as either i) high improvement in pain or function or ii) moderate improvement in at least 2 of the 3 domains (pain, function, and Patient’s Global Assessment).

In this trial, OMERACT-OARSI response will be determined using WOMAC pain and function index scores and the PGA described in Section 7.3.3.

